**SAMPLE SIZE CALCULATIONS AND STATISTICAL POWER**

The primary endpoint is the need for a repeat injection. Based on historic data, about 50% of individuals who receive a steroid injection return for an additional injection within six months due to pain. Assuming a significance level of 0.05 and a need for a repeat injection in the AF arm of 10%, with 60 total patients (30 per arm), we have about 90% power to detect a difference in need for repeat injections at 6 months between the two arms. Expecting approximately 5 randomizations per week, 60 patients will take approximately 3 months to enroll.

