**OUTCOMES OF THE STUDY**

### **Primary Endpoint**

- The need for a repeat allogeneic intra-articular injection [Time Frame: 6 months].

Participants in both the SOC and pAF treatment arms may require and/or request rescue medication (i.e. SOC injection) at any time and will be given per PI discretion as part of standard of care. The clinicians will not know which study arm the study participant is in but will treat the participant with the SOC injection. This information will be documented and collected in the Electronic Medical Record (EMR), as well as the study's electronic data capture system. Participants will not be given any additional pAF injections throughout the 12-month study period.

The participant will continue to be treated with SOC injections as needed. The outcome will be an indicator of whether or not a subject received a rescue medication within 6 months. Sensitivity analyses will also be performed to assess the number of rescue medications given over the course of a year.

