**DATA ANALYSIS**

The primary endpoint (need for a repeat injection) will be compared between the two arms using Fisher's Exact test. An alpha 0.05 will be used as the threshold for statistical significance. Missing data will remain missing rather than be imputed since this is a pilot study assessing preliminary safety and feasibility.

The secondary endpoint (pain) will consist of a comparison of mean values for VAS scoring scales pre-injection and at follow-up visits at 1, 3, 6 and 12-months. Clinically significant outcomes will be determined based on the minimal clinically important difference (MCID) occurring for each respective scale, which is defined as the smallest change score needed for the effect to be considered clinically relevant.

Continuous secondary and exploratory endpoints will be compared between arms using Wilcoxon Rank Sum tests. Categorical endpoints (including safety outcomes) will be compared between arms using Chi-squared tests. In cases of small counts, exact tests may be used.

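### The stated power of about 90% is right for complete data but has no margin for loss; Boschloo's exact test would add power at the same 5% error limit

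*Combined protocol and SAP*

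**What the plan says.** The primary outcome is binary. The Primary Endpoint section says: "The outcome will be an indicator of whether or not a subject received a rescue medication within 6 months". The Data Analysis section names the test, "The primary endpoint (need for a repeat injection) will be compared between the two arms using Fisher's Exact test", and the threshold, "An alpha 0.05 will be used as the threshold for statistical significance". On incomplete data it says: "Missing data will remain missing rather than be imputed since this is a pilot study assessing preliminary safety and feasibility".

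The sample size section takes its steroid rate from historic data ("about 50% of individuals who receive a steroid injection return for an additional injection within six months due to pain"), assumes 10% for the pAF arm without giving a source, and concludes that "with 60 total patients (30 per arm), we have about 90% power to detect a difference in need for repeat injections at 6 months". That section names no test, does not say whether alpha is one- or two-sided, and makes no allowance for loss.

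Two other passages bear on loss. The Randomization section keeps every randomised subject in the intention-to-treat analysis, treated or not. The Primary Endpoint section has rescue injections recorded in the medical record as well as in the study database.

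**The concern.** The power figure counts all 60 randomised participants. Under the no-imputation rule, anyone whose 6-month status is unknown drops out of the 2×2 table, so the delivered power depends on how many outcomes are known. Withdrawal is allowed at any time. After the 1-month visit, scheduled follow-up is by questionnaire sent by mail, email or text. Some loss is therefore foreseeable, and the design has no stated margin for it.

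Fisher's test conditions on the total number of events. With 30 per arm this makes it markedly conservative, so part of the allowed 5% error buys no power. In a trial this small, that unused alpha could supply some of the missing margin without enrolling anyone. It matters most if the pAF rate is higher than the assumed 10%.

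**Working it through.** **Inputs.** Rates of 50% (steroid) and 10% (pAF), alpha 0.05 and 30 per arm come from the sample size section; Fisher's test comes from Data Analysis. Two-sided testing is my assumption, because the documents do not state it. All loss rates are also assumptions.

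**Formulas.** With n1 steroid and n2 pAF participants analysed, and x and y events:

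- Power = Σ over all (x, y) of Bin(x; n1, 0.50) × Bin(y; n2, 0.10) × 1[p(x, y) ≤ 0.05].
- Exact type I error = the same sum with one common rate π in both arms, maximised over π from 0.001 to 0.999.
- Boschloo's test takes Fisher's p-value as the ordering statistic. It rejects in the largest region of that ordering whose maximum type I error is at most 0.05. This region contains Fisher's, so it rejects whenever Fisher's does.

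**Step 1: the plan's own figure, 30 per arm.**

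- Two-sided Fisher: 91.4%.
- Normal approximation, pooled variance, mean rate 0.30: z = (0.40√30 − 1.96√(2 × 0.3 × 0.7)) / √(0.25 + 0.09) = (2.191 − 1.270) / 0.583 = 1.58, giving 94.3%.
- Normal approximation with continuity correction: 89.7%.
- One-sided Fisher at 0.05: 95.4%.

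The stated figure matches two-sided Fisher or the continuity-corrected formula.

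**Step 2: power with equal arms, 50% against 10%.**

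| Analysed per arm | Lost per arm | Fisher | Boschloo |
|---|---|---|---|
| 30 | 0 | 91.4% | 93.0% |
| 29 | 1 | 90.0% | 94.1% |
| 28 | 2 | 89.1% | 93.1% |
| 27 | 3 (10%) | 87.2% | 92.0% |
| 26 | 4 (13%) | 85.5% | 91.1% |
| 25 | 5 (17%) | 83.3% | 89.5% |
| 24 | 6 (20%) | 83.4% | 87.8% |

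Exact power moves in steps, so small reversals between neighbouring sizes are genuine.

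**Step 3: unequal arms (steroid/pAF).**

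| Split | Fisher | Boschloo |
|---|---|---|
| 30/29 | 92.0% | 93.5% |
| 30/28 | 92.7% | 94.1% |
| 28/30 | 92.4% | 93.4% |
| 27/28 | 91.8% | 92.9% |
| 26/27 | 90.3% | 91.7% |
| 27/26 | 88.1% | 89.9% |
| 24/28 | 89.8% | 89.8% |

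The gain is about 1 to 1.8 points in most slightly unequal splits and nil in a few. Averaged over independent random loss, Fisher power is 91.2% at 5% loss, 89.5% at 10%, 87.4% at 15% and 85.0% at 20%.

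**Step 4: type I error.** At 30/30 Fisher's maximum is 2.74%; it is 2.61% at a common rate of 30% and 0.94% at 10%. The maximum is higher in unequal splits: 3.6% at 30/29, 3.7% at 30/28, 3.8% at 27/28 and 4.4% at 25/24. Boschloo's maximum is 4.5% to 4.9% at the equal-arm sizes above.

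**Step 5: a smaller effect.** If the true pAF rate is 20%, power at 30/30 is 59.6% with Fisher and 67.1% with Boschloo, a gain of 7.5 points. At 27/27 it is 55.0% against 62.7%. The 30/30 comparison needs no attrition assumption.

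**The case against.** The strongest reply is that the plan contains no error. Its figure is approximate, the named test gives 91.4%, and even at 10% random loss the average of 89.5% is fairly described as about 90%. This stands: the calculation is sound.

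A reader might infer that 90% power fails once more than one participant per arm is lost. That is true only when the arms stay equal. At 26/27, with four and three lost, Fisher power is still 90.3%. Equal arms are where Fisher's discreteness costs most.

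A reader might also count Fisher's conservatism as a further, hidden loss. It is not, because the stated figure agrees with Fisher's own power and so already includes it. Nor is half the alpha always unused; that describes 30/30, and unequal splits use more.

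Loss of the primary outcome may also be smaller than questionnaire non-response, because rescue injections are captured in the medical record. The documents give no loss rate, so 10% and 20% are illustrations.

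Finally, Fisher's test is valid and familiar, and at 30/30 under the design rates Boschloo adds only 1.7 points (91.35% to 93.04%). That is fair. The case for changing rests on the larger gains if arms stay equal after loss or if the effect is smaller than assumed, and on the change costing no participants.

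**Conclusion.** The point holds as an improvement to the analysis, not as a correction of a wrong figure. The stated power is right for complete data, two-sided Fisher, and 50% against 10%. It has little margin: with equal arms the shortfall becomes material at about 27 per arm (87.2%), and averaged over random loss at about 15% to 20% (87.4% to 85.0%).

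Boschloo's test supplies some of that margin with type I error still held at 5%. With equal arms it keeps at least 90% down to 26 per arm. The documents do not support the stronger claim that it recovers any loss: it gives 89.5% at 25 per arm and 87.8% at 24, and adds little in some unequal splits. Its clearest benefit is 67.1% against 59.6% at full enrolment if the pAF rate is 20%, since the 10% is the design assumption with no stated source.

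The conclusion rests on a two-sided alpha, on independent binomial outcomes, and on participants with unknown status leaving the comparison.

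**What to change.** In Data Analysis, before unblinding, replace Fisher's test for the primary 2×2 comparison with Boschloo's exact unconditional test at two-sided 0.05. Report the risk difference with a 95% CI, and name the interval method.

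Restate the power paragraph with the test, the two-sided alpha, and power for complete data and for assumed 10% and 20% loss. For equal arms of 30, 27 and 24, Boschloo gives 93.0%, 92.0% and 87.8%. Label the loss rates as assumptions, and say whether the medical record will establish 6-month status when a questionnaire is missing.

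The cost is one sentence in the analysis section and a rewritten paragraph. Standard software has the test, and no participants are added. The drawbacks are a less familiar test and a stated power that visibly depends on follow-up. The choice should be made before unblinding, because a later switch would look driven by the data.

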**DATA MANAGEMENT**

**Clinical Site Data Management**

The clinical site will maintain study records in locked file cabinets. The site will maintain an Essential Documents Binder, which may be in paper or electronic form. Copies of all informed consent documents will be kept on file and be available for site monitoring inspection (on site or remote).

**DATA COORDINATING CENTER**

The Data Coordinating Center (DCC) in the Department of Pediatrics at the University of Utah School of Medicine provides data coordination and management services for a variety of national research networks. Anchoring these services is a state-of-the-art, energy efficient data center. The data center facility supports more than 3500 users around the country and provides a secure, reliable, enterprise-wide infrastructure for delivering mission critical DCC systems and services.

The data center was built using high industry standards and energy efficient cooling solutions. The data center is cooled by an LCP (Liquid Cooling Package) inline cooling technology; providing efficiency, redundancy and the modularity required. Cooling is based upon a hot/cold aisle design that allows for

**A Phase I/II Randomized, Double-Blinded Standard of Care (Corticosteroid vs Sterile Amniotic Fluid for Osteoarthritis**

**PI: [name].**

**Version: 5.00 dated 23MAY2023**

even air distribution with minimal hot spots. The data center electrical power system contains an uninterruptible power system (UPS) with a diesel backup generator. The data center is protected with a FM200 fire suppression system to act as a secondary system to the smoke detectors. The data center provides enhanced security to safeguard the equipment and the data within in it. Entry into the data center is restricted by card access and layered security measures and controls. The data center and external building access points are monitored with video surveillance.

The data center has a virtualized environment. The virtual environment consists of more than 400 virtual servers and nearly 25 physical servers. The data center's virtualization solution provides key advantages; 1) high availability – in the event of hardware failure, virtual servers automatically go back online in a seamless process. 2) flexible infrastructure – disk storage, memory and processor capacity can be increased or reallocated at any time. 3) rapid deployment – servers can be provisioned on-demand.

Production servers running mission critical applications are clustered and configured for failover events. Servers are backed up with encryption through a dedicated backup server. Our storage area networking (SAN) applications, clusters, and switch-to-switch links are on a 10 gigabit network. Incremental backups occur Monday through Friday. A full system backup occurs weekly. Full backups are taken off site on a weekly basis to an off-site commercial storage facility. The data center currently manages over 150 terabytes of data.

Our information systems are available 24 hours a day, 7 days a week to all users, unless a scheduled maintenance interruption or mitigation of an unexpected event is required. If this occurs, we notify all users of the relevant systems, and data entry can be deferred until after the interruption is over. Our critical systems availability has exceeded 99.9% for the past two years.

**Security, Support, Encryption and Confidentiality**

The data center coordinates the network infrastructure and security with University Information Technology (UIT) at the University of Utah. This provides us with effective firewall hardware, automatic network intrusion detection, and the expertise of dedicated security experts working at the University. Centralized authentication and communication over public networks is encrypted using transport layer security (TLS) or virtual private network (VPN) technologies, both of which provide at least 128 bit encryption. Direct access to data center machines is only available while physically located inside our offices, or via a VPN client.

All network traffic is monitored for intrusion attempts, security scans are regularly run against our servers, and our IT staff are notified of intrusion alerts. Security is maintained with Windows user/group domain-level security. Users are required to change their passwords every 90 days. All files are protected at user/group levels; database security is handled in a similar manner with group-level access to databases, tables, and views in Microsoft SQL Server. Finally, all laptop computers in use in the DCC/division are whole-disk encrypted.

The data center uses control center tools to continuously monitor systems and failure alerts. Environmental and network systems are also monitored to ensure up time. And highly trained system administrators on staff are available to respond in high risk emergency events.

**A Phase I/II Randomized, Double-Blinded Standard of Care (Corticosteroid vs Sterile Amniotic Fluid for Osteoarthritis**

**PI: [name].**

**Version: 5.00 dated 23MAY2023**

All personnel involved with data coordinating centers have signed confidentiality agreements concerning data encountered in the course of their daily work. All personnel (including administrative staff) have received Human Subjects Protection and Health Information Portability and Accountability Act (HIPAA) education. We require all users to sign specific agreements concerning security, confidentiality, and use of our information systems, before access is provided.

**ELECTRONIC DATA CAPTURE SYSTEM**

The Data Coordinating Center (DCC) will develop an electronic data capture system for this trial. Currently the DCC uses multiple applications, such as OpenClinica or REDCap, and will elect to use the most appropriate application at the time of implementation of the study. Data will be entered by the clinical site.

The DCC will use an electronic discrepancy management system to notify sites of inconsistent or erroneous data entry, which will be corrected by the clinical site. The discrepancy management system maintains an audit trail of all discrepancy resolution.

**STUDY MONITORING**

The investigators recognize the importance of ensuring data of excellent quality. Study monitoring is critical to this process. Monitoring has been a very effective tool for maintaining data quality in previous Data Coordinating Center studies, and we will utilize this process to ensure excellent quality data in the proposed study. The DCC utilizes risk-based methodology to identify and correct problems that may arise at sites. The risk-based approach to monitoring focuses on oversight activities and preventing or mitigating key risks to data quality, as well as to processes critical to human subject protection and integrity of the trial or study.

Study monitors must be provided with appropriate access to study materials and the medical records for study subjects. If the medical records are in electronic form, the clinical investigator or an authorized individual must provide any assistance necessary to facilitate the study monitor's review of data in the electronic medical record.

**Site Monitoring Plan**

A supplemental study-specific risk-based monitoring plan, separate from the protocol will be completed which outlines specific criteria for monitoring. This plan may include the number of planned site visits, criteria for focused visits, additional visits or remote monitoring, a plan for chart review and a follow up plan for non-compliant sites, if applicable. The monitoring plan also describes the type of monitoring that will take place (e.g., sample of all subjects within a site; key data or all data), the schedule of visits, how they are reported and a time frame to resolve any issues found.

**Clinical Site Monitoring**

Site monitoring visits may be performed by a trained site monitor during the study period to ensure regulatory compliance, patient safety, and to monitor the quality of data collected. Essential document binders, regulatory documents and data collection forms may be reviewed. Interim visits will take place depending on budget, site enrollment, and compliance issues identified. The site monitor will provide each site with a written report, and sites will be required to follow up on any deficiencies. It is anticipated that the study monitoring visits for this protocol will consist of a site initiation visit (prior to

**A Phase I/II Randomized, Double-Blinded Standard of Care (Corticosteroid vs Sterile Amniotic Fluid for Osteoarthritis**

**PI: [name].**

**Version: 5.00 dated 23MAY2023**

patient enrollment), interim visits, and a close out visit. The site initiation may take place as group training made up of site investigators and research assistants.

**Remote Monitoring**

The Data Coordinating Center may supplement on-site monitoring with remote monitoring activities. Remote monitoring involves detailed review of the data entered by the Clinical Center and consultations with the Clinical Center investigator and/or research coordinator to review safety and data quality. This may require uploading copies of medical records, patient study specific regulatory documentation, or other source documents for the monitor to review. Alternatively, other methods, such as remotely viewing source documentation, may be utilized. This helps assure protocol compliance and accurate data collection. The Data Coordinating Center may conduct more remote monitoring activities early in the trial to assure protocol compliance and identify any training issues that may exist. Remote monitoring documents will be retained in accordance with federal requirements. Safety of subjects will be monitored and ensured in accordance with the Data and Safety Monitoring Board (DSMB) plan.

**Pharmacy Monitoring**

The Cell Therapy and Regenerative Medicine (CTRM) must maintain adequate records of all dispensed study drug. The CTRM may be monitored and requested to send copies of these documents to the Data Coordinating Center.

**Record Access**

The medical record and study files (including informed consent documents) must be made available to authorized representatives of the Data Coordinating Center, upon request, for source verification of study documentation. In addition, medical information and data generated by this study must be available for inspection upon request by representatives (when applicable) of the Food and Drug Administration (FDA), other Federal funders or study sponsors, and the Institutional Review Board (IRB).

**PROTECTION OF HUMAN SUBJECTS**

**Institutional Review Board (IRB) Approval**

IRB approval must be obtained prior to participating in the study. The Data Coordinating Center will track IRB approval status and will not permit subject enrollment without documentation of initial IRB approval and maintenance of that approval throughout subsequent years of the project.

**Informed Consent**

For all subjects  $\geq 18$  years of age, informed consent is required. Subjects who are capable of giving consent and who are alert and competent, will be asked, following an appropriate discussion of risks and benefits, to give consent to the study. For those with diminished mental capacity, a Legal Authorized Representative will be used.

**Potential Risks**

Loss of confidentiality of the subject is a potential risk of the study; however, safeguards are in place to protect against this.

Regarding loss/breach of privacy and confidentiality, all applicable parties (e.g. clinical sites, DCC) will be responsible for ensuring that appropriate data security procedures are in place.

**A Phase I/II Randomized, Double-Blinded Standard of Care (Corticosteroid vs Sterile Amniotic Fluid for Osteoarthritis**

**PI: [name].**

**Version: 5.00 dated 23MAY2023**

**Potential Benefits**

The benefits of active drug therapy in this population are unknown; however, it is postulated that there may be a potential benefit in pain and functional outcomes for patients with osteoarthritis of the knee.

**DATA AND SAFETY MONITORING PLAN**

**Data Safety Monitoring Board (DSMB)**

The study will have a Data Safety Monitoring Board (DSMB). The DSMB will have a charter, will approve the protocol prior to implementation, and will review interim analyses as applicable. The purpose of the DSMB is to advise the sponsors and Principal Investigator(s) regarding the continuing safety of study subjects and the continuing validity and scientific merit of the study. The DSMB is responsible for monitoring accrual of study subjects, adherence to the study protocol, assessments of data quality, performance of the individual Clinical Center, review of serious adverse events and other subject safety issues, and review of formal interim statistical analyses of treatment efficacy.

**ADVERSE EVENT REPORTING**

The site investigator is responsible for evaluating all adverse events at their Clinical Center and ensuring that they are properly reported. All adverse events will be captured during the study period. The nature of each experience, date and time (where appropriate) of onset, outcome, course, and relationship to treatment will be documented.

